12.2 Participant demographics and other baseline characteristics

Demographic and other baseline data including disease characteristics will be listed by cohort and treatment group and summarized descriptively by treatment group for each cohort, Cohorts 1 and 2 pooled), and all cohorts pooled for the FAS and Safety set if Safety set is different from FAS.

Categorical data will be presented as frequencies and percentages. For continuous data, mean, standard deviation, median, minimum, and maximum will be presented. For selected parameters, 25th and 75th percentiles will also be presented.

Relevant medical histories and current medical conditions at baseline will be summarized by system organ class and preferred term, and treatment group for each cohort, Cohorts 1 and 2 pooled and all cohorts pooled for the FAS period.

12.3 Treatments

The Safety set will be used for the analysis below. Categorical data will be summarized as frequencies and percentages. For continuous data, mean, standard deviation, median, 25th and 75th percentiles, minimum, and maximum will be presented.

The duration of exposure in number of doses and days to IV cipargamin (KAE609), IV artesunate, and Coartem will be summarized by means of descriptive statistics.

Concomitant medications and significant non-drug therapies prior to and after the start of the study treatment will be listed by cohort and treatment group and summarized according to the Anatomical Therapeutic Chemical (ATC) classification system, by treatment group for each cohort and all cohorts pooled.

12.4 Analysis of the primary endpoint(s)/estimand(s)

The primary objective is to show that IV cipargamin is non-inferior to IV artesunate in the proportion of participants with $\geq 90\%$ *P. falciparum* parasite reduction at 12 hours. These will be evaluated within each Cohort separately except Cohort 1, which will be combined with Cohort 2. The analysis will be performed on the FAS.

12.4.1 Definition of primary endpoint(s)/estimand(s)

A participant is considered as achieving $\geq 90\%$ reduction in *P. falciparum* parasite from baseline at 12 hours (after the first IV dose) if *P. falciparum* asexual parasite reading at 12 hours is either absent or with a positive value that is $\leq 10\%$ of the baseline value. See [Section 2.1](#) for detailed definition of estimand.

12.4.2 Statistical model, hypothesis, and method of analysis

The statistical null hypothesis is that the difference in proportion of participants with $\geq 90\%$ reduction at 12 hours between a cipargamin dose regimen and artesunate is ≤ -0.1 with the alternative hypothesis that the difference is > -0.1 .

The statistical hypothesis will be tested at the 2-sided 10% significance level without multiplicity adjustment for multiple comparison due to multiple cipargamin dose regimen. Two-sided 90% confidence intervals (CI) for the difference between each cipargamin dose regimen vs artesunate will be provided using the Wilson uncorrected method based on FAS; a cipargamin dose regimen is said to be non-inferior to artesunate if the lower limit of CI is > -0.1 .

The hypothesis will be tested for each Cohort separately except Cohort 1, which will be combined with Cohort 2.

Data from participants in Cohorts 1 and 2 will be pooled together to allow evaluation of non-inferiority to artesunate since both cohorts include participants aged ≥ 12 years although participants in Cohort 1 are milder in clinical condition compared to participants in Cohort 2. The underlying assumptions are (1) the participants for each treatment group follow a binomial distribution separately in each Cohort separately except Cohort 1, which will be combined with Cohort 2 (2) participants for each treatment group, follow the same binomial distribution in Cohorts 1 and 2.

12.4.3 Handling of intercurrent events of primary estimand

The primary estimand will account for the different intercurrent events as follows:

- If a participant receives any IV rescue antimalarial medication prior to the *P. falciparum* asexual parasite assessment at 12 hours, the participant will be classified as not achieving $\geq 90\%$ reduction,
- If a participant dies prior to the *P. falciparum* asexual parasite assessment at 12 hours, the participant will be classified as not achieving 90% reduction.

Composite strategy is used to handle intercurrent events as the intercurrent events indicate that the study IV treatment is not working quickly enough to prevent clinical deterioration.

12.4.4 Handling of missing values not related to intercurrent event

All participants should be hospitalized at the time of 12 hours post treatment unless death or discontinuation from the study have occurred. Death is considered as an intercurrent events and is handled in [Section 12.4.3](#). Any missing data not related to intercurrent events will be handled according to [Table 12-1](#).

Since participants are hospitalized at 12 hours, these missing data should be rare. After receiving the IV study medication, a participant's parasite load should decrease over time such that the parasite count is lower at 12 hours than at previous visits (6 hours or earlier). That is, the probability that a participant achieves at least 90% parasite reduction is higher at 12 hours than at 6 hours. Therefore, the imputation of using parasite assessment at the latest visit prior to 12 hours is conservative. This imputation may slightly under estimate the proportion of participants with at least 90% parasite reduction at 12 hours.

Table 12-1 Handling of other events that may occur and affect derivation of primary endpoint

Event	Outcome
Discontinuation of study prior to parasite assessment at 12 hours, such as withdrawal of consent, COVID-19, etc.	Impute using the latest assessment prior to 12 hours including baseline. Note: the outcome is 'no' if baseline value is used.
Intermediate parasite count missing at 12 hours due to other reason (such as missing sample, technical reason, etc.)	

12.4.5 Sensitivity analyses for primary endpoint/estimand

After receiving antimalarial medication, a participant's parasite usually decreases log-linearly after a lag stage ([White 2011](#), [Flegg et al 2011](#)). For artemisinin derivatives, parasitemia starts to decline in a log-linear manner almost as soon as parasiticidal drug concentrations are reached ([White 2011](#)). The T_{max} is about 0.5 to 15 minutes for IV artesunate ([Artesunate PI](#)). The T_{max} is about 4 hours for oral cipargamin and should be much shorter for IV cipargamin. Missing data of parasite counts at 12 hours could be well estimated using a log linear interpolation of the 2 parasite counts immediate before and after 12 hours. Since there are 3 planned parasite assessments on or after 2 hours, missing parasite count at 12 hours due to early discontinuation could be estimated using participant specific log linear regression if there are at least 2 parasite counts prior to the discontinuation. A sensitivity analysis will be performed using interpolation for missing data at intermediate time points and extrapolation using a log linear regression if there are at least 2 parasite counts prior to discontinuation. In the event that a participant does not have at least 2 parasite counts prior to discontinuation, the participant will be imputed as not achieving $\geq 90\%$ reduction at 12 hours. Parasite counts below the limit of detection will be substituted using the half limit of detection.

The severity of disease is different between Cohort 1 and Cohort 2, which might impact the ability to achieve $\geq 90\%$ parasite reduction, ie., resulting in a different binomial distribution between Cohorts 1 and 2. Therefore, two-sided 90% confidence intervals (CI) for the difference between each IV cipargamin dose regimen vs IV artesunate will be provided for Cohort 1 and Cohort 2 separately, using handling of missing values not related to intercurrent events specified in [Section 12.4.4](#) and in this section.

12.4.6 Supplementary analysis

For each Cohort (except Cohort 1, which will be pooled with Cohort 2), the difference between a cipargamin dose regimen and artesunate in the proportion of participants with $\geq 90\%$ reduction in parasite at 12 hours will be performed using the Fisher exact test.

For each cipargamin dose regimen that is selected for Cohorts 3-5, the difference versus artesunate in proportion of participants with $\geq 90\%$ reduction in parasite at 12 hours will be evaluated by pooling data from all cohorts to show if the IV cipargamin dose regimen is superior to IV artesunate. The treatment difference will be evaluated based on 2-sided 95% CIs using a Mantel-Haenszel estimate of the common risk difference stratified by cohort (Cohorts 1 and 2 will be pooled together and used as a single stratum)(SAS manual version 13.2). P-values will be provided using a Cochran-Mantel-Haenszel test (CMH) stratified by cohort.

Similarly, between treatment difference will be evaluated in children by repeating the above supplemental analysis on pooled Cohorts from 3-5 only.

These supplement analyses target a different hypothesis to show superiority of each cipargamin dose regimen over artesunate and will be performed using the FAS and handling of missing values not related to intercurrent events according to [Section 12.4.4](#) and [Section 12.4.5](#).

12.4.7 Supportive analyses

The analyses specified in [Section 12.4.2](#), [Section 12.4.5](#) and [Section 12.4.6](#), will be repeated using the PPS.

12.5 Analysis of secondary endpoints/estimands

Secondary endpoints will be descriptively presented and tabulated (n, mean, standard deviation, median, minimum, and maximum for continuous variables; n and percent for categorical variables) by treatment group for each cohort separately. Cohort 2 will be also evaluated together with Cohort 1. For stratified analysis, Cohort 1 will be combined with Cohort 2. The cipargamin dose regimen that is dropped after reviewing data from Cohorts 1-2 will be included only in the by-cohort analyses. For those treatment groups that are selected for Cohorts 3-5, descriptive statistics will be provided by treatment group using all pooled Cohorts (1-5) as well as separately pooled Cohorts 3-5. When data from different cohorts are pooled, an IV cipargamin regimen in Cohorts 3 to 5 (aged < 12 years) will be analyzed together with the equivalent IV cipargamin regimen as used in Cohorts 1 and 2 (aged ≥ 12 years). Such an IV cipargamin dose regimen will be denoted and labeled using the same cipargamin treatment group.

12.5.1 Efficacy and/or Pharmacodynamic endpoint(s)

Secondary efficacy endpoints include:

- Clinical success at 24 hours, 48 hours, 72 hours, 96 hours, hospital discharge, Day 6, Day 8, Day 15, Day 22, and Day 29. See [Table 8-3](#) for detailed information of defining clinical success. Clinical success at H48 is considered as a key secondary endpoint with a secondary estimand.
- Individual signs of severe malaria over time
 - Altered consciousness - Prostration or GCS < 11 for participants > 5 years old or BCS < 3 for participants ≤ 5 years old
 - Renal Impairment- Serum creatinine > 3 x ULN or > 3 mg/dL or need for renal replacement therapy
 - Acidosis- Serum lactate > 4 mmol/L
 - Respiratory distress – present or absent
 - Severe anemia- Hb < 5 g/dl or Hb < 7g/dl in pediatric and adults respectively with parasite count of > 10,000/μl or need of blood transfusion
 - Jaundice- Serum bilirubin > 3 g/dl with parasite count of > 100,000/μl
 - Hypoglycemia- plasma glucose < 40 mg/dL
- Proportion of participants with convulsion developing or persisting > 6 hour after start of IV study treatment
- Proportion of participants developing any new severe malaria signs (as per WHO severe malaria criteria) after treatment
- Proportion of participants with neurological sequelae at Day 2
- Proportions of participants with ≥ 90% *P. falciparum* asexual parasite reduction from baseline at 24 and 48 hours
- *P. falciparum* asexual parasite reduction ratios (PRR) at 12, 24 and 48 hours
- Time to *P. falciparum* asexual parasite clearance (PCT) (in hours), defined as time from the first IV study medication until the first total and continued disappearance of asexual parasite forms which remained at least a further 48 hours,

- Time to fever clearance (FCT) (in hours), defined as time from the first IV study medication until the first time the axillary body temperature decreased below and remained below 37.5°C axillary or 38.0°C oral/tympanic/rectal for at least a further 24 hours,
- Time to recover from prostration (in hours)
- PCE slope half-life
- Proportion of participants with recrudescence and reinfection by Day 29

Analysis of secondary estimand

The clinical success at 48 hours (see [Table 8-3](#)) for definition of clinical success and [Section 2.2](#) for definition of estimand) will be evaluated using the FAS with data from all cohorts pooled.

Intercurrent events and other non-intercurrent events including partial missing data that may occur and affect the derivation of secondary estimand will be handled in [Section 12.2](#). Note: partial data missing should be rare since participants are still hospitalized at 48 hours.

Table 12-2 Handling of intercurrent events and other events that may occur and affect the derivation of secondary estimand

Event	Outcome
Receive IV antimalarial rescue medication prior to 48 hours	Not clinical success
Discontinue the study prior to 48 hours, such as withdrawal of consent, COVID-19, etc.	Not clinical success due to early discharge
Missing parasite assessment at 48 hours ^{\$}	
 • Not clinical success if asexual parasites present in the latest visit prior to 48 hours • Ignored* otherwise
Altered consciousness: missing Prostration, missing Glasgow Coma Score or missing Blantyre coma score in relevant age groups ^{\$}	Use the result from the latest visit prior to 48 hours (including baseline) for each missing item
Renal impairment: missing SCr ^{\$}	
 • Not clinical success if Renal Replacement Therapy is used at 48 hours • Use the latest SCr prior to 48 hours
Acidosis and respiratory distress: missing plasma lactate or missing respiratory distress assessment ^{\$}	Use the result from the latest visit prior to 48 hours (including baseline) for each missing item
* determination of clinical success depends on other assessments.	
^{\$} Partial data missing, unlikely since participants are in the hospital	

Two-sided 90% confidence intervals (CI) for the proportion of participants with clinical success at 48 hours will be provided based on the exact method (Clopper-Pearson method). In addition, 2-sided 90% CIs for the difference between a cipargamin dose regimen and artesunate will be provided using a Mantel-Haenszel estimate of the common risk difference stratified by cohort where Cohorts 1 and 2 will be combined. Mantel-Haenszel estimate is a weighted risk difference with weight roughly proportional to strata size. It's an unbiased estimation of risk difference in the population under the following assumptions either (1) the risk difference is

same across different strata or (2) the strata sizes in study resemble the strata size in the disease population at large.

For participants who discontinue the study prior to the H48 assessments, such as withdrawal of consent, COVID-19, etc, the worst outcome (not clinical success) is used. This may underestimate the clinical success rate at 48 hours. A sensitivity analysis will be performed by imputing missing outcome using the best outcome as "Clinical success".

Descriptive statistics will be provided by cohort in addition to all cohorts pooled.

Supplementary analysis for secondary estimand

Analysis defined for secondary estimand will be repeated by pooling all participants from Cohorts 3-5.

Analysis of clinical success at timepoints other than 48 hours

The clinical success defined in [Table 8-3](#) at Hours 24, 72, and 96, at hospital discharge, Days 8, 15, 22, and 29 will be evaluated using the FAS and data from all cohorts pooled.

Intercurrent events and non-intercurrent events that may occur and affect the derivation of clinical success are handled in [Table 12-3](#).

Table 12-3 Handling of other events that may occur and affect the derivation of clinical success at a visit other than 48 hours

Event	During hospital period (H24,72, and 96, and hospital discharge)[§]	After discharge from hospital (Days 8, 15, 22, and 29)
Receive IV antimalarial rescue medication prior to the visit	Not clinical success	Not clinical success
Death not related to malaria (as per adjudication committee)	Not applicable	Use the worst clinical success outcome between the hospital discharge visit and the last available visit
Discontinue the study prior to the visit due to other reasons, such as withdrawal of consent, lost to follow-up, COVID-19, etc.	Not clinical success due to early discharge	Use the worst clinical success outcome between the hospital discharge visit and the last available visit
Skipping the visit	Use the worst clinical success outcome from the visit before or visit after	Use the worst clinical success outcome from the visit before or visit after
Missing parasite assessments with visit	
 Not clinical success if asexual parasites present in the previous visit Ignored* otherwise 	
 Not clinical success if asexual parasites not cleared at the hospital discharge or parasites reappearance in a previous visit Ignored* otherwise

Event	During hospital period (H24,72, and 96, and hospital discharge)[§]	After discharge from hospital (Days 8, 15, 22, and 29)
Altered consciousness: missing Prostration, missing Glasgow Coma Score in adults or missing Blantyre coma score in children	Use the latest visit (including baseline) prior to the visit for each missing item	
 • Not clinical success if prostration or coma is reported as AEs for the visit • Ignored* otherwise
Renal impairment: missing SCr	
 • Not clinical success if Renal Replacement Therapy is used at the visit • Use the latest SCr prior to the visit 	
 • Not clinical success if Renal Replacement Therapy is used at the visit • Not clinical success if renal failure or renal impairment is reported as AE for the visit • Ignored* otherwise
Acidosis and respiratory distress: missing plasma lactate or missing respiratory distress assessment	Use the result from the latest visit prior to the visit for each missing item	
 • Not clinical success if lactic acidosis or respiratory distress is reported as AE for the visit • Ignored* otherwise
[§] Partial data missing is unlikely prior to hospital discharge [*] Participant is considered as clinical success unless the participant does not meet clinical success due to other criterion		

At each visit, 2-sided 90% CIs for the proportion of participants with clinical success for each treatment group will be provided based on the exact method. In addition, 2-sided 90% CIs for the difference between a cipargamin dose regimen and artesunate will be provided using a Mantel-Haenszel estimate of the common risk difference stratified by cohort where Cohorts 1 and 2 will be combined.

At each visit, 2-sided 90% CIs for the proportion of participants with clinical success for each treatment group will be provided based on the exact method and 2-sided 90% CIs for treatment difference vs artesunate will be provided using the Wilson uncorrected method by cohort. For death not related to malaria and discontinuation of study after the hospital discharge, the following 2 sensitivity analyses will be performed:

- Use the last available clinical success outcome prior to death or discontinuation.
- Use multiple imputation methods, which will be specified in the statistical analysis plan.

Analyses of clinical and laboratory assessments and signs related to severe malaria

All analyses described below will be performed using the FAS without imputation for missing assessments, ie., missing assessments will be excluded from analysis.

For the following individual signs of severe malaria, the shift table of post-baseline presence relative to baseline presence or not will be provided by visit (24 hours, 48 hours, 72 hours, 96 hours, at hospital discharge, Day 6, Day 8, Day 15, Day 22, and Day 29), cohort, and treatment group:

- Altered consciousness - Prostration or GCS < 11 for age > 5 yrs / BCS < 3 for age ≤ 5 years
- Renal Impairment- Serum creatinine > 3 x ULN or > 3 mg/dL or need for renal replacement therapy
- Acidosis- Serum lactate > 4 mmol/L
- Respiratory distress – present or absent
- Severe anemia- Hb < 5 g/dl or Hb < 7g/dl in pediatric and adults respectively with parasite count of > 10,000/μl or need of blood transfusion
- Jaundice- Serum bilirubin > 3 g/dl with parasite count of > 100,000/μl
- Hypoglycemia- plasma glucose < 40 mg/dL

Number and percent of participants will be provided by cohort and treatment group for the following events related to severe malaria:

- Convulsion developing or persisting > 6 hour after the IV study treatment. Note: “persisting > 6 hour” means that convulsion is present at baseline and again at a visit that is > 6 hours after IV study treatment.
- New severe malaria signs (as per WHO severe malaria criteria) after the IV study treatment
- Neurological sequelae (by adjudication) at Day 29

Neurological Examination results will be summarized descriptively by visit, cohort, and treatment group.

For the following time to event variables, the first visit with the event will be used to calculate the time if a participant experiences the event. If a participant does not experience the event, the time will be censored at the last visit assessment for specific type of event (such as last sit assessment, etc.) with the exception of date of discontinuation (or death) for time to oral antimalarial therapy.

- Time to oral antimalarial therapy (in hours),
- Time to recover prostration in participants who are prostrated at baseline

Descriptive statistics will be provided using the Kaplan-Meier method and Kaplan-Meier curves will be presented by cohort and treatment.

Day of discharge from hospital will be summarized descriptively by cohort and treatment group. Day of death will be used in case of death during hospitalization.

Analysis of secondary endpoints related to parasite clearance dynamics

All analyses will be performed using the FAS.

Proportions of participants with ≥ 90% *P. falciparum* asexual parasite reduction from baseline at 24 and 48 hours: missing data due to intercurrent and non-intercurrent events will be handled similar to the primary efficacy endpoint (See [Section 12.4.3](#), [Section 12.4.4](#)). These 2 variables will be analyzed using the statistical methods specified in [Section 12.4.2](#), [Section 12.4.5](#) and [Section 12.4.6](#).

PRRs at 12, 24 and 48 hours: PRR is defined as the ratio of asexual parasite at baseline divided by asexual parasite at post-baseline. If the asexual parasite count at post-baseline is 0, the half value of detection limit will be used to calculate the ratio. Missing values will not be imputed. For each PRR, 2-sided 90% CIs for each treatment group and for treatment ratio between each IV cipargamin regime vs IV artesunate by cohort will be provided using an analysis of covariance (ANCOVA) model on the log scale with log baseline value as a covariate and treatment group as a factor. For all cohorts pooled, the analysis will be performed with cohort as an additional factor in the ANCOVA model.

PCT and FCT: PCT will be calculated based on uncorrected *P. falciparum* asexual parasite counts. If a participant does not experience an event (such as *P. falciparum* parasite clearance, etc.), the time to the event will be censored at the last relevant assessment (such as last *P. falciparum* parasite assessment, etc.) participants who do not have the health condition at baseline (eg, fever, etc.) will be excluded from the corresponding time to event analysis (eg., FCT, etc.). Descriptive statistics will provided using the Kaplan-Meier method and Kaplan-Meier curves will be presented by treatment and cohort. For all cohorts pooled, difference for the cipargamin regimen vs artesunate will be evaluated using a log-rank test stratified by cohort. Two-sided 90% CIs for the hazard ratio will be provided.

PCE slope half-life: PCE slope half-life will be calculated for each participant using the WWARN (World Wide Antimalarial Resistance Network) Parasite Clearance Estimator as described in [Flegg et al 2011](#). 2-sided 90% CIs for each treatment group and for treatment ratio between each IV cipargamin regime vs IV artesunate by cohort will be provided using an analysis of covariance (ANCOVA) model on the log scale with log baseline value as a covariate and treatment group as a factor. For all cohorts pooled, the analysis will be performed with cohort as an additional factor in the ANCOVA model.

Incidence of recrudescence and reinfection during the study

Reinfection is defined as appearance of asexual parasites after clearance of initial infection with a genotype different from those parasites present at baseline.

Recrudescence is defined as appearance of asexual parasites after clearance of initial infection with a genotype identical to that of parasites present at baseline. Recrudescence must be confirmed by PCR analysis.

Incidence rates of recrudescence and reinfection at Study Day 29 will be estimated by Kaplan-Meier method based on the subset of FAS participants who have clearance of initial infection by Study Day 7. Time to recrudescence/reinfection will be calculated from the time of first IV study medication to the date of first event if a participant experience the event and be censored at the time of last parasite assessment if a participant does not experience the event.

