 - Drug interrupted/withdrawn
6. its outcome (i.e. recovery status or whether it was fatal)

Conditions that were already present at the time of informed consent should be recorded in medical history of the participant.

Adverse events (including lab abnormalities that constitute AEs) should be described using a diagnosis whenever possible, rather than individual underlying signs and symptoms.

Adverse event monitoring should be continued until the end of study visit.

Once an adverse event is detected, it must be followed until its resolution or until it is judged to be permanent (e.g. continuing at the end of the study), and assessment must be made at each visit (or more frequently, if necessary) of any changes in severity, the suspected relationship to the interventions required to treat it, and the outcome.

Information about adverse drug reactions for the investigational drug can be found in the [Investigator's Brochure](#). For comparator and oral standard of care treatments, safety-related information is listed in the product information.

Abnormal laboratory values or test results constitute adverse events only if they fulfill at least one of the following criteria:

- they induce clinical signs or symptoms
- they are considered clinically significant
- they require therapy

Clinically significant abnormal laboratory values or test results must be identified through a review of values outside of normal ranges/clinically notable ranges, significant changes from baseline or the previous visit, or values which are considered to be non-typical in participants with the underlying disease.

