Altered consciousness – Prostration (inability to sit or drink or breast feed) or GCS < 11 for patients > 5 years / BCS < 3 for patients ≤ 5 years of age. Prostration, GCS/ BCS is recorded by investigator in the relevant CRF. In case that a patient completes the visit but the data are missing, this will be determined to be ‘yes’ if a patient has an AE of “Altered state of consciousness” with starting day since previous visit to the current visit and ‘no’ otherwise.

Renal Impairment - Serum creatinine > 3xULN or > 3 mg/dL or need for renal replacement therapy (RRT). Serum creatinine is recorded in the point of care devices (POC) or using local lab in case of non-availability of POC and renal replacement is recorded by investigator in the concomitant CRF. In case that a patient completes the visit but the serum creatinine is missing, this will be determined to be ‘yes’ if a patient has an “renal replacement” concomitant with starting day since previous visit to the current visit and ‘no’ otherwise.

Acidosis - Plasma lactate ≥ 4 mmol/L (In database, lactate is captured under lactic acid) or Respiratory distress. Plasma lactate is recorded in the point of care devices (POC) or using local lab in case of non-availability of POC and respiratory distress is recorded by investigator in the severe malaria CRF. In case that a patient completes the visit but the data are missing, this will be determined to be ‘yes’ if a patient has an AE of “Respiratory distress” with starting day since previous visit to the current visit and ‘no’ otherwise.

Single imputation rule:

Following single imputations will be performed before applying the multiple imputations:

After a patient has parasite clearance, any intermediate missing parasite between 2 negative parasite assessments is imputed as negative parasite assessment since it is very likely that the intermediate missing should also be negative as prior and post missing data show negative result.

Once a patient died before hospital discharge or is declared as malaria related death at a timepoint, the patient will be considered as not achieving the clinical success for the timepoint onwards.

If a patient has parasite reappearance after the hospital discharge, the patient is considered as not achieving the clinical success for the timepoint onwards.

If a patient receives IV antimalarial rescue medication prior to hospital discharge, the patient is considered as not achieving the clinical success for the timepoint onwards.

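### After discharge, Table 12-3 can fail a missing smear on discharge-day parasites that later smears had cleared, and can pass a missing organ-sign item whose last value was abnormal

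*Protocol*

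**What the plan says.** Protocol Table 8-3 defines clinical success as status at a time point: alive, no asexual parasites, and no key sign of severe malaria. Table 12-3 (Protocol 12.5.1) says what to do when a component is missing at a visit other than 48 hours. SAP Table 2-4 (2.7.2.1) repeats its rules.

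- **Smear, in hospital:** "Not clinical success if asexual parasites present in the previous visit"; otherwise the gap is ignored.
- **Smear, after discharge:** "Not clinical success if asexual parasites not cleared at the hospital discharge or parasites reappearance in a previous visit"; otherwise ignored.
- **Creatinine, in hospital:** renal replacement at the visit is a failure; otherwise "Use the latest SCr prior to the visit". The consciousness, lactate and respiratory items also take the latest earlier result.
- **Creatinine, after discharge:** renal replacement at the visit is a failure, as is an adverse event: "Not clinical success if renal failure or renal impairment is reported as AE for the visit". Otherwise ignored.
- **Consciousness, after discharge:** "Not clinical success if prostration or coma is reported as AEs for the visit"; otherwise ignored.
- **Lactate or respiratory distress, after discharge:** "Not clinical success if lactic acidosis or respiratory distress is reported as AE for the visit"; otherwise ignored.

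The table's footnote makes an ignored item a success unless some other criterion fails. A wholly skipped visit takes the worse of the visits before and after.

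**The concern.** In hospital, a gap is filled from what was last seen in that participant. After discharge, the same gap is filled in two other ways, which err in opposite directions. A smear result from discharge day can outweigh several later negatives. An abnormal organ-sign value at the last measurement is not consulted at all.

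Clinical success at Days 8, 15, 22 and 29 would then be misclassified for some participants. The protocol is assessing this composite as a candidate Phase III endpoint (1.2 and 8.3.3), so its derivation should be coherent at every visit where it is reported.

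**Working it through.** The plan attaches no figure to these rules, so there is none to reproduce. The check applies the rules literally and sets them beside each other.

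**1. Can a participant be discharged with parasites?** Yes. Footnote 1 of Tables 8-1 and 8-2 asks only for oral eligibility and the investigator's opinion, from 72 hours. The 72-hour rescue criterion in Protocol 6.2.1 requires parasites together with inability to take oral treatment, so parasites alone do not meet it.

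**2. Smear rule.** Take smears at discharge and Days 6, 8 and 15, each positive (+) or negative (−), with Day 22 missing. There are 2 × 2 × 2 × 2 = 16 histories.

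| Last smear (Day 15) | Histories | Scored failure | Scored pass |
|---|---|---|---|
| Positive | 8 | 8 | 0 |
| Negative | 8 | 7 | 1 (all negative) |

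Of the 7 failures with a negative last smear, 4 contain a reappearance (− − + −, − + − −, − + + −, + − + −). The other 3 fail solely because of the discharge smear (+ − − −, + + − −, + + + −). In those 3, parasites cleared after discharge and never returned.

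**3. Organ-sign rule, item missing at an attended visit, no other criterion failing.**

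| Last observed value | AE or RRT recorded | Table 12-3 | If an abnormal last value also counted |
|---|---|---|---|
| Normal | No | Success | Success |
| Normal | Yes | Failure | Failure |
| Abnormal | No | Success | Failure |
| Abnormal | Yes | Failure | Failure |

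The third row can arise because of Protocol 10.1.1: "Conditions that were already present at the time of informed consent should be recorded in medical history of the participant". Renal impairment that brought a participant into the trial and then persisted need not be an adverse event.

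**4. Against the skipped-visit rule.**
- Smears + at discharge, − on Days 6 and 8, lost on Day 15, − on Day 22. Attending Day 15 gives failure. Skipping Day 15 gives success if Days 8 and 22 were successes.
- Creatinine abnormal on Day 8, missing on Day 15, no adverse event or renal replacement. Attending Day 15 gives success if all else is met. Skipping it gives failure.

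**5. Against SAP 5.8.4.** Once a patient has cleared, "any intermediate missing parasite between 2 negative parasite assessments is imputed as negative parasite assessment". For the 3 histories isolated in step 2, a negative Day 29 smear makes the missing Day 22 smear negative here and a failure under Table 2-4. Section 5.8.4 also calls for the imputations of earlier sections before multiple imputation, without an order of precedence. For a missing creatinine at a completed visit it uses renal replacement only, without the renal adverse-event trigger of Table 2-4. For consciousness and respiratory distress it counts only adverse events that began since the previous visit.

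**6. Size per participant** (arm sizes from Protocol 12.8.2): 1/116 = 0.86 points pooled (1/107 = 0.93 if 107 are evaluable); 1/38 = 2.6 points in Cohort 3 or 4; 1/20 = 5 points in Cohort 5.

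**7. Illustrative range for the smear rule.** Assume 5–15% of artesunate and about 0% of cipargamin participants are parasitaemic at discharge, and 2–10% of smears are missing at an attended visit. None of these figures is in the documents. The products are 0.05 × 0.02 = 0.1 point and 0.15 × 0.10 = 1.5 points. Both treat every such case as misclassified, so 1.5 points is a ceiling under these inputs.

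**The case against.** The smear rule does not disregard the last result. Its reappearance clause, with the discharge condition, fails every history that ends in a positive smear, so the rule is conservative. That stands: the fault is confined to a negative last smear that cannot undo discharge-day parasitaemia.

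A reader might infer that the rule favours cipargamin, since SAP 5.8.4 expects a median clearance above 40 hours on artesunate and found most oral-cipargamin patients clear by 24 hours. The same paragraph adds that after 48 hours all artesunate patients may be negative, and discharge is no earlier than 72 hours. The assumed contrast of 5–15% against 0% also builds in the direction it then reports. A directional claim is not supported.

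A reader might also want simply to use the last smear. That would delete the reappearance clause, although SAP 5.8.4 treats reappearance after discharge as failure from then on. This objection stands, and the fix keeps the clause.

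The organ-sign route is narrow. The sign must persist past discharge, the item must be missing at an attended visit, and no adverse event may be recorded, although 10.1.1 makes a clinically significant laboratory abnormality an adverse event. Individual signs are also tabulated from observed data, so persistence stays visible. Using adverse-event information instead of a week-old value may have been deliberate. These points limit the frequency. They do not explain why an abnormal last value should count as resolved, and no rationale is given.

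**Conclusion.** The point holds as a defect of the post-discharge column for a single missing item at an attended visit. Discharge-day parasitaemia can fail a participant who has since cleared, and a persisting entry sign can be scored as resolved. The skipped-visit rule and SAP 5.8.4 give different answers for the same participant.

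The effect per affected participant is about 0.9 points in a pooled arm, 2.6 points in an arm of 38 and 5 points in an arm of 20. The smear rule could weigh more on the slower-clearing arm. Without rates of discharge-day parasitaemia or of missing items, neither the net direction nor the size can be established, and the organ-sign rule cannot be bounded at all. The two sensitivity analyses address non-malaria death and discontinuation after discharge, so they do not test these rules.

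The primary endpoint and the 48-hour key secondary endpoint use other tables and are not affected. The affected time points carry no pre-specified hypothesis. This is worth correcting, but it does not threaten the trial's main conclusions.

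**What to change.** In the post-discharge column of Protocol Table 12-3 and SAP Table 2-4:

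- **Missing smear:** score failure if the most recent earlier smear was positive, or if parasites reappeared after discharge. Let negative smears after discharge supersede discharge-day parasitaemia.
- **Missing consciousness, creatinine, lactate or respiratory item:** also score failure if the most recent observed value of that item was abnormal. Keep the adverse-event and renal-replacement triggers.

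State the same rules, and their order of precedence, in SAP 5.8.4.

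Of the 16 smear histories in the working, this changes 3 from failure to pass and leaves the 4 with reappearance as failures. Of the four organ-sign combinations, it changes one from success to failure.

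The cost is rewording four cells in each document and one part of SAP 5.8.4, with no new data. The drawback is that an abnormal value may be carried forward after it has resolved. With visits at Days 8, 15, 22 and 29 that value would be up to about a week old, or older if the item is missing at consecutive visits.
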